- 3. Severe other diseases which started before the "study pregnancy" and lasted into the "study pregnancy" period, including congenital heart disease, arrhythmia, history of myocardial infarction (MI), history of stroke, or active cancer
- 4. Serious physical injury that occurred during the "study pregnancy": severe car collision injury, serious injury at home/work, etc. Multiple gestation (i.e., pregnancy with more than one baby at a time, such as pregnancy with twins, triplets, and quadruplets) in the "study pregnancy"

Study Design and Recruitment

Study group: Study group participants will be recruited from Nerivio's user base. An invitation message will be sent via in-app notification and/or email to all Nerivio users who are (1) female, AND (2) between 18 and 42 years of age as of November 1st, 2019 - March 31st, 2021. Users who meet these criteria will be invited to fill in a screening and eligibility questionnaire. If they meet the eligibility criteria, they will be offered the opportunity to participate in the study. Participants will complete and sign an electronic informed consent form. Following consent, participants will be asked to complete the questionnaire. Once complete, participants will be compensated for their time.

Control group: Control group participants will be referred to the study by site co-investigators, who are US licensed healthcare providers seeing women with headache disorders and/or women during their pre-pregnancy and/or pregnancy period. Patients interested in participating will be directed to the same screening and eligibility questionnaire and will follow the same study design.

Endpoints

Endpoints focus on the health of the mother and the baby, during pregnancy and three months postpartum.

Primary endpoint:

Demonstrate that the study group is not different than the control group in regard to gestational age at delivery (measured in pregnancy weeks).

QMS document

TCH-011 Clinical Study Protocol

Doc ID: TECXXXX

Revision #: 1.0

Page: 6 of 25

Secondary endpoints:

Demonstrate that the study group is not different from the control group in:

- 1. Baby's birth weight (average birth weight)
- 2. Miscarriage rate (% of miscarriage cases)
- 3. Preterm birth rate (% cases of preterm pregnancies, as measured in % of pregnancy weeks less than 37)
- 4. Birth deficits rate (% of birth deficits)
- 5. Still births rate (% of still births)

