- 6. Meeting developmental milestones following 3 months postnatal (% of babies)
- 7. Visits to the emergency room or urgent care due to pregnancy and/or migraine symptoms during pregnancy and 3 months postpartum period (# of events)

Exploratory endpoints: Difference between the study group and the control group in:

- 1. Overall subjective **feeling of safety** using acute migraine treatments during pregnancy (in subjects who used such treatments).
- 2. Overall subjective **satisfaction** with the acute migraine therapies used during the pregnancy (in subjects who used such treatments).
- 3. APGAR score at 5 minutes.

Data analysis

Statistical Hypothesis

The goal of the proposed study is to test the null hypothesis that treating with Nerivio during pregnancy does not impose a safety risk relative to standard care migraine treatment for pregnant women. In other words, the hypothesis is that the means of the two populations are equal. Thus, in this study, the following hypotheses will be tested:

• Null hypothesis: H0: GAt = GAc

• Alternate hypothesis: H1: GAt ≠ GAc

Where GAt and GAc are the average Gestational Age in the study group and control group, respectively. If the null hypothesis is not rejected, the study will be deemed successful. The criterion for significance has been set at 0.05. The test is 2-tailed.

TCH-011 Clinical Study Protocol

Doc ID: TECXXXX

Revision #: 1.0

Page: 7 of 25

Planned Sample Size

Based on USA data from 2020 [Osterman M, et al. Births: Final Data for 2020. Natl Vital Stat Rep. 2021] we assume mean gestational age (GA) of 38.4 with standard deviation of 2.7 (range 26-42).

With the proposed sample size of 114 for each group, the study will have power of 80% to yield a statistically significant result. This computation assumes that the mean difference is less than 1.0 week, and the common within-group standard deviation is 2.7. This effect was selected as the smallest effect that would be important to detect.

Precision for estimating the effect size: We further estimate the mean difference between the two populations. On average, a study of this design would enable us to report the mean difference with a precision (95% confidence level) of plus/minus 0.70 weeks.

Given this statistical requirement up to 400 participants will be recruited per group.

Statistical Analysis Plan

Data will be collected from all patients recruited to the study. Data analysis will not include patients who are:

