Appendix 2: Survey Questionnaire

This questionnaire asks about your general health with a focus on your migraine, your health during and after your "study pregnancy", and about your child's health.

Please refer to your latest, completed, pregnancy (if you are currently pregnant, please do not refer to the current pregnancy when answering the following questions). We will refer to the latest, completed, pregnancy as the "study pregnancy".

It will take approximately 30-40 minutes to complete the questionnaire.

Part 1 – Demographics and medical history prior to "study pregnancy"

1. What is your date of birth?

Mark on Calendar

- 2. Are you of Hispanic, Latino, or of Spanish origin?
 - Yes
 - No
- 3. How would you describe yourself?
 - American Indian or Alaska Native
 - Asian
 - Black or African American
 - Hispanic or Latino
 - Native Hawaiian or Other Pacific Islander
 - White or Caucasian
 - Other
- 4. What is your height (feet, inches)

Choose: Pull down menu between 4.0 to 7.0 with 0.1 jumps. Allow other.

5. Weight (lb) at the beginning of your study pregnancy

Choose: Pull down menu between 85 and 300 lb, with jumps of 5 units. Allow other.

6. Do you have a history of any of the following medical conditions, that was diagnosed prior to your study pregnancy? Check all that apply

QMS document

TCH-011 Clinical Study Protocol

Doc ID: TECXXXX
Revision #: 1.0

Page: 13 of 25

AIDS/	/HIV
-------------------------	------

- Anemia
- Asthma
- Autoimmune disease (such as lupus, rheumatoid arthritis etc)
- Clinically diagnosed depression or any other psychiatric diseases
- Clinical obesity (body mass index, BMI, greater than 30)
- Endometriosis
- Epilepsy
- Kidney disease
- High blood pressure
- Pre-pregnancy diabetes
- Polycystic ovary syndrome (PCOS)
- Sexually transmitted disorders
- Thyroid disease
- Other diseases
 - Please specify _____

Check all that applies

- 7. Prior to your "study pregnancy", do you have a history of (Check all that applies)
 - Smoking
 - Excessive alcohol consumption (more than 1 glass of wine/day or any other alcohol equivalent)
 - Using medical marijuana
 - Using recreational drugs

Multiple choice

- 8. On average, how many days per month did you experience migraine in the 6 months prior to the "study pregnancy"?
 - Less than 4 days per month
 - 4-8 days per a month

QMS document

TCH-011 Clinical Study Protocol

Doc ID: TECXXXX

Revision #: 1.0

Page: 14 of 25

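### Birth weight is compared only as a raw group average between non-randomised groups; an adjusted comparison, plus a labelled weight-for-weeks description, could be added from data already collected

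*Combined protocol and SAP*

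**What the plan says.** Under Endpoints, the first secondary endpoint is "Baby's birth weight (average birth weight". It belongs to a list meant to show that the groups do not differ. No listed endpoint expresses weight relative to gestational age. Low birth weight appears only as an answer option under newborn complications (Appendix 2, question 45).

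The groups are formed by recruitment source (Study Design and Recruitment): "Study group participants will be recruited from Nerivio's user base", and "Control group participants will be referred to the study by site co-investigators".

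The section headed Statistical Analysis Plan consists of exclusions, introduced by "Data analysis will not include patients who are". It states no model, covariate or adjustment for any endpoint.

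Under Planned Sample Size the inputs concern gestational age only: "we assume mean gestational age (GA) of 38.4 with standard deviation of 2.7". The size is given as "With the proposed sample size of 114 for each group", and then "up to 400 participants will be recruited per group". There is no birth-weight SD, effect size or precision.

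Appendix 2 collects:
- height (question 4) and "Weight (lb) at the beginning of your study pregnancy" (question 5);
- high blood pressure and pre-pregnancy diabetes (question 6), and smoking history (question 7);
- earlier pregnancies (questions 15 and 16);
- gestational age in weeks and days (question 20) and baby's sex (question 42);
- birth weight in classes (question 43): below 1.5 kg, 1.5 to 2.49 kg, 100 g steps to 4 kg, and above 4 kg.

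**The concern.** Two things limit what a raw average can tell the reader.

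First, app users of a device and patients referred by clinics may differ in body size, blood pressure, diabetes, smoking and parity. All of these can bear on birth weight. A raw difference, or its absence, mixes any device effect with those differences, although the survey records them.

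Second, birth weight combines length of gestation with growth for the weeks reached. The primary endpoint and the preterm rate cover early delivery; no listed endpoint covers growth. A raw deficit cannot show which occurred, and longer gestation in one group could hide poorer growth.

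Birth weight is the only listed endpoint based on the baby's size at birth. It has no decision rule and does not determine study success, so what is at stake is the reading of this one endpoint.

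**Working it through.** **The plan's own figure.** For gestational age with SD 2.7 and a 1.0-week difference, n per group = 2 × (1.96 + 0.84)² × 2.7² / 1.0² ≈ 114.4, against 114 stated. The half-width is 1.96 × 2.7 × √(2/114) = 0.70 weeks, as stated. Neither figure concerns birth weight.

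**Assumptions, because the plan gives none for birth weight.** SD 550 g; correlation r with gestational age 0.3 to 0.7; gestational-age SD 2.7 weeks (from the plan); exact weights; linear relation.

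**Raw comparison.** Half-width = 1.96 × 550 × √(2/n): 143 g at 114 per group, 76 g at 400. At 114 per group, SD 500 to 600 g gives 130 to 156 g.

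**What conditioning on gestational age does.** The residual SD is 550 × √(1 − r²): 525, 476 or 393 g for r = 0.3, 0.5 or 0.7. At 114 per group the half-width becomes 136, 124 or 102 g. This interval belongs to a different quantity, the difference at equal gestational age.

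To see the consequence, split a deficit into a direct part and a part acting through gestation. The slope is r × 550 / 2.7, which is 102 g per week at r = 0.5. The raw standard error is 550 × √(2/114) = 72.8 g. The adjusted one is 476 × √(2/114) = 63.1 g, marginally larger when gestation differs. Power is two-sided at 0.05 by t-test, 114 per group, r = 0.5:

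| How the deficit arises | Expected raw difference | Expected adjusted difference | Power raw | Power adjusted |
|---|---|---|---|---|
| 150 g direct, equal gestation | −150 g | −150 g | 54% | 66% |
| 75 g direct, 0.75 week shorter (0.75 × 102 = 76 g) | −151 g | −75 g | 54% | 22% |
| None direct, 1 week shorter | −102 g | 0 g | 29% | 5% |

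The pattern holds across the range of r. With equal gestation, adjusted power is 58% at r = 0.3 and 82% at r = 0.7. With 150 g split evenly, the slopes are 61 and 143 g per week, so gestation is 75/61 = 1.23 or 75/143 = 0.53 week shorter. Adjusted power is then about 18% or 30%, against 54% raw.

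**Bias from shared causes.** Suppose an unmeasured cause, present in a share p of pregnancies, shortens gestation by a weeks and lowers weight by a further g grams. Let dp be the group difference in p, and e the gestation difference from unrelated reasons. Then:
- k = −a·p(1−p) / (a²·p(1−p) + 2.6²), where 2.6 weeks is the assumed remaining SD;
- bias = −g × (dp − k × (e − a·dp)), positive in Nerivio's favour.

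With p 0.1 to 0.2, a 1 to 4 and g 150 to 300:
- dp = 0, e = −0.5 to −1.0: about 1 to 21 g in Nerivio's favour. At the upper corner k = −0.64/9.32 = −0.069, and 300 × 0.069 = 20.6 g.
- e = 0, dp = ±0.05: about 5 to 15 g in either direction. The raw difference is then shifted too.

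**Pre-pregnancy factors.** The documents give no distribution of these factors by group and no relation to weight. The confounding removed, or precision gained, by adjusting for them cannot be computed here.

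**The case against.** The strongest reply is that this is a preference. The raw mean is a valid total-effect summary, the plan states no model for any endpoint, and missing adjustment would matter more for the primary endpoint. This stands as far as it goes: there is no error in the stated endpoint, and the point is optional.

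The second reply concerns precision. A reader might infer that, because gestational age predicts weight and is collected, conditioning on it makes this endpoint more precise or more powerful. The documents do not support that. Gestational age is measured after exposure and is itself the primary endpoint, so the narrower interval answers another question. The power gain needs equal gestation in both groups. In a study that aims to show no difference, an estimate that moves towards zero when harm acts through shorter gestation could reassure wrongly. This objection stands in full and determines the form of the fix.

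The third reply is that shared causes of gestation and weight are partly recorded: pregnancy-induced hypertension (question 23) and smoking during the pregnancy (question 25). These relate to the pregnancy itself and do not belong among the pre-pregnancy covariates. They do show that the second model's shared-cause problem is not wholly unmeasured, and the caveat should say so.

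Finally, the raw average also needs a stated rule for the open and wide classes in question 43. That is correct and belongs in the same sentence of the plan.

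**Conclusion.** The point holds as a low-severity suggestion. The plan compares birth weight by raw average between two differently recruited groups. The data for an adjusted comparison, and for a description of weight given weeks reached, are already collected.

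Three stronger readings go too far. The raw mean is not wrong. Adjustment for gestational age is not a more powerful version of this endpoint: under the assumptions above, power can rise from 54% to 66% or fall to 22%, depending on how the deficit arises. And pre-pregnancy covariates do not remove the confounding from different recruitment sources; they address measured differences only.

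Every birth-weight figure rests on an assumed SD and correlation. The benefit of the pre-pregnancy adjustment cannot be quantified from the documents. Sample size, primary endpoint and success rule are unaffected.

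**What to change.** For live births, keep the raw mean difference, with a stated rule for the classes in question 43, and add two interval regressions on those classes.

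1. **Adjusted total-effect comparison.** Group, baby's sex (question 42), height and starting weight (questions 4 and 5), high blood pressure and pre-pregnancy diabetes (question 6), smoking history (question 7) and parity (questions 15 and 16). Report the difference with its 95% CI beside the raw one, and state that only measured confounding is reduced.
2. **Description of weight given weeks reached.** The same model plus gestational age (question 20) with a non-linear term, labelled descriptive. Its use is to help tell earlier delivery from poorer growth.

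State with model 2 that gestational age is post-exposure and is the primary endpoint; that the estimate moves towards zero when harm acts through shorter gestation; that shared causes may bias it in Nerivio's favour; and that it must not be used alone to claim no difference. Make no claim of added precision or power from it.

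The cost is a short paragraph in the analysis section and two extra models. No new data or participants are needed. The main risk is that model 2 is misread as evidence of safety, which the caveat is there to prevent.

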TCH-011 Clinical Study Protocol

Doc ID: TECXXXX
Revision #: 1.0

Page: 16 of 25

PIO	locoi	

- Botox® injection for migraine prevention (Botulinum toxin)
- Aimovig[®] (Erenumab)
- Ajovy® (Fremanezumab)
- Emgality® (galcanezumab-gnlm)
- Vyepti® (eptinezumab-jjmr)
- Nurtec® ODT (Rimegepant)
- Devices (e.g., gammaCore, Cefaly)
- Other
- Did not use any preventive treatment

Check all that applies

- 12. Have you been diagnosed with migraine with aura by a licensed healthcare provider? (Aura is a neurologic symptom that occurs typically before or during migraine that lasts 5-60 minutes and is characterized by an evolution of neurologic symptoms such as flashing lights or colors that grow in your visual field)
 - Yes
 - No
- 13. Do you usually experience aura right before your headache attacks?
 - Always
 - Sometimes
 - Never
- 14. Have you ever used Nerivio® to treat your migraine attacks?
 - Yes
 - No
- 15. How many prior pregnancies before the "study pregnancy" have you had?

Choose from 0 to 10 and "more than 10"

16. How many of these were completed pregnancies?

QMS document

TCH-011 Clinical Study Protocol

Doc ID: TECXXXX

Revision #: 1.0

Page: 17 of 25

Show question if >0 in the previous question. Responses: Choose from 0 to 10 and "more than 10"

- 17. Is there a family history of congenital defects or malformations?
 - Yes
 - No

Part 2 – Study pregnancy

The following questions refer to you latest, completed, pregnancy, termed "study pregnancy" (if you are currently pregnant, please do not refer to this pregnancy when answering the questionnaire).

- 18. What was the first day of the last menstrual period (LMP) before your "study pregnancy"? (Please provide accurate month and year. If you do not recall the exact day within the month, please choose 1st day of the month).
 - Choose on calendar / enter date (month, year; day is optional)

Year and month are good enough. Day is optional.

- 19. What was the delivery date of your "study pregnancy"?
 - Choose on calendar
- 20. What was your baby's gestational age at delivery or at the end of pregnancy (pregnancy length measured by number of weeks and days) of your "study pregnancy"

Choose on "roller", allow weeks (6 to 42 weeks) and days (+0 to 6 days). If possible, allow weeks and days separately..

- 21. What is the status of your "study pregnancy"?
 - Live birth
 - Elective termination
 - Spontaneous abortion (or miscarriage)
 - Late fetal death

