- 22. If you had a miscarriage, what was its cause?
 - I did not experience a miscarriage
 - Abnormal fetal development

QMS document

TCH-011 Clinical Study Protocol

Doc ID: TECXXXX

Revision #: 1.0 Page: 18 of 25

- Abnormal placenta (such as abruption)
- Blood disorders such as thrombophilias
- Cervical insufficiency
- Chromosomal abnormalities
- Maternal anatomic abnormalities such as uterine fibroids, polyps or adhesions in uterus
- Physical trauma
- Unknown cause
- Other

23. Delivery circumstances (Check all that applies)

- Spontaneous labor
- Induction of labor
- Past due date
- Decreased fetal movement
- Cardiac arrhythmia in fetus
- Pregnancy induced hypertension such as gestational hypertension or pre-eclampsia
- HELLP syndrome
- Premature rupture of membranes
- Other complications or medical concerns

Check all that apply

24. What was the mode of delivery?

- Repeat Cesarean Delivery
- Primary Cesarean delivery
- Spontaneous vaginal delivery

25. During your "study pregnancy", did you do any of the following (select all that apply)

Smoking

QMS document

TCH-011 Clinical Study Protocol

Doc ID: TECXXXX Revision #: 1.0

Page: 19 of 25

•	Excessively consuming alcohol (more than 1 glass of wine/day or any other
	equivalent)

- Using recreational drugs

Using medical marijuana

Check all that apply

26. Was the baby discharged from the hospital at the same time with yo	u?
--	----

- Yes
- No
- 27. Did you use Nerivio to treat your migraine attacks during your "study pregnancy"?
 - Yes
 - No
- 28. During your "study pregnancy", did you use Nerivio for migraine treatment at least 3 times?
 - Yes
 - No

Part 3 – Migraine during the study pregnancy

The following questions refer to your latest, completed, pregnancy referred to as the "study pregnancy" (if you are currently pregnant, please do not refer to this pregnancy when answering the questionnaire).

- 29. How many migraine days per month (on average) did you have during the FIRST trimester of your "study pregnancy"?
 - Less than 4 days per month
 - 4-8 days per a month
 - 9-14 days per month
 - 15 days or more per month

Multiple choice

30. How often did you use ACUTE treatments for migraine during the FIRST trimester of your "study pregnancy"?

QMS document

TCH-011 Clinical Study Protocol

Doc ID: TECXXXX

Revision #: 1.0

Page: 20 of 25

- Less than 4 times per month
- 4-8 times per a month
- 9-14 times per month
- 15 times or more per month

Multiple choice

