Part 5 – Baby's health

- 42. For your "study pregnancy", what is your baby's sex at birth?
 - Male
 - Female
- 43. What was the baby's birth weight (lbs)?

Choose on a drop-down menu, including the following answers:

- Less than 1.5 kg / 3.4 pounds
- Between 1.5 and 2.49 kg / between 3 pounds 4 ounces and 5 pounds 8 ounces
- Weights with jumps of 100 gram up to 4 kg and the equivalent in pounds (2.5, 2.6, 2.7, 4)
- More than 4 kg / 8 pounds and 13 ounces

QMS document

TCH-011 Clinical Study Protocol

Doc ID: TECXXXX
Revision #: 1.0

Page: 24 of 25

44.	Was	the	baby	diagnosed	with	any	birth	defects?
-----	-----	-----	------	-----------	------	-----	-------	----------

- No
- Yes
- 45. Were there any complications with the baby after delivery?
 - No
 - Yes

If Yes, what type of complication?

- Neonatal jaundice,
- Newborn required admission to the neonatal intensive care unit
- Respiratory distress syndrome
- Infection such as sepsis
- Failure to thrive
- Low birth weight
- Other
- 46. Did your baby meet routine developmental milestones at 3 months? of life (such as smiling, gurgle, visually tracking objects, and rolling over within the first 3 months)
 - No
 - Yes
- 47. What was your baby's APGAR scores at 1 minute after birth?

We know it might be difficult to remember this score. Please check your discharge notes to find the 1 minute APGAR score, although not all notes include this information:

- Choose 1-10
- Don't know / Can't find the 5 min APGAR score

Use a dropdown menu, and add the option can't find

48. What was your baby's APGAR scores 5 minutes after birth? We know it might be difficult to remember this score. Please check your discharge notes to find the 5 minutes APGAR score, although not all notes include this information:

QMS document

TCH-011 Clinical Study Protocol

Doc ID: TECXXXX

Revision #: 1.0

Page: 25 of 25

- Choose 1-10
- Don't know / Can't find the 5 min APGAR score

Use a dropdown menu, and add the option can't find

- 49. Does the baby have any additional APGAR scores at 10, 15 or 20 minutes?
 - Yes
 - No
 - Don't know

If Yes, go to the next page, and ask for APGAR scores at 3 additional time points. Otherwise (answer: No or Don't know), go directly to the last page.

Page break

- 50. What was your baby's APGAR scores 10 minutes after birth? We know it might be difficult to remember this score. Please check your discharge notes to find the 5 minutes APGAR score:
 - Choose 1-10

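### The birth-defect endpoint rests on one untyped yes/no question about the baby, so reported defects cannot be classified and those in terminated or lost pregnancies may be missed

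*Combined protocol and SAP*

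**What the plan says.** The Endpoints section introduces the secondary endpoints with "Demonstrate that the study group is not different from the control group in" and lists the fourth as "Birth deficits rate (% of birth deficits"). It gives no case definition, denominator or margin, and does not separate structural from chromosomal or major from minor findings.

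The relevant items in Appendix 2 are:

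- **Q44** (Part 5, on the baby's health): "Was the baby diagnosed with any birth defects", answered No or Yes. There is no follow-up, and no skip rule is shown.
- **Q45**, the next item, on complications after delivery, continues with "If Yes, what type of complication" and a list.
- **Q21** allows four pregnancy outcomes: live birth, "Elective termination", miscarriage and late fetal death.
- **Q22** asks "If you had a miscarriage, what was its cause". Its options include abnormal fetal development and chromosomal abnormalities. Nothing links these answers to endpoint 4.

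No item asks why a pregnancy was terminated or why a late fetal death occurred. The documents describe no record check or adjudication of reported defects.

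**The concern.** The study's goal is safety in pregnancy, and birth defects are among its main fetal-safety outcomes. The endpoint as measured has two weaknesses.

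1. **Pooling.** Every reported diagnosis counts the same, whatever its type. A chromosomal disorder, which a treatment used during the pregnancy would not be expected to cause, adds to the rate exactly as a structural malformation does. So does a minor finding, provided it was diagnosed.
2. **Missed cases.** A woman whose pregnancy was terminated after a prenatal anomaly diagnosis, or ended in late fetal death, meets a question about the baby. She may answer Yes, answer No or leave it blank, and the analyst cannot tell how she read it.

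The aim is to show that the groups do not differ, with no margin, so a noisy outcome makes a finding of no difference easier to reach. An untyped Yes cannot be classified later without going back to the participant, and the plan describes no such step.

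**Working it through.** **The plan's own figure.** Planned Sample Size gives 114 per group for gestational age (difference 1.0 week, SD 2.7, 80% power), and the test is set by "The criterion for significance has been set at 0.05. The test is 2-tailed". The normal formula gives 2 × (1.960 + 0.842)² × 2.7² / 1.0² = 114.4, so 115 per group, and power at 114 is 79.8%. The figure reproduces but covers gestational age only. No rate, margin or power is given for endpoint 4, so every defect rate below is an assumption.

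**Pooling, equal in both groups.** Assume relevant defects of 3% in controls and 9% in the Nerivio group, plus a share *u* of unrelated Yes answers in each.

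- Observed ratio = (0.09 + *u*) / (0.03 + *u*).
- Power (arcsine, two-sided 0.05) = Φ(*h*·√(*n*/2) − 1.96), with *h* = 2·arcsin√p₂ − 2·arcsin√p₁.
- For *u* = 0, *h* = 0.261. For *u* = 0.04, *h* = 0.202.
- 95% half-width of the difference = 1.96·√[(p₁(1−p₁) + p₂(1−p₂))/*n*].

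| *u* | Ratio | Difference (points) | Power, n=114 | Power, n=400 | Half-width, n=400 (points) |
|---|---|---|---|---|---|
| 0 | 3.0 | 6 | 50% | 96% | 3.3 |
| 2% | 2.2 | 6 | 40% | 89% | 3.7 |
| 4% | 1.86 | 6 | 33% | 82% | 4.1 |
| 6% | 1.67 | 6 | 29% | 75% | 4.5 |

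The ratio shrinks and power falls. The difference stays at 6 points but is estimated less precisely.

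**Missed cases, equal in both groups.** If a share *m* is missed in each group, the ratio is 2p(1−*m*) / p(1−*m*) = 2 for a true doubling, so it is unchanged. The difference shrinks by the factor (1−*m*). For 3% versus 6% at 400 per group (normal approximation for two proportions):

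| Scenario | Observed ratio | Power | N per group for 80% power |
|---|---|---|---|
| Complete and typed | 2.0 | 53.5% | 749 |
| 20% missed in both groups | 2.0 | 44.5% | 945 |
| 3% unrelated findings added to both | 1.5 | 36.3% | 1209 |
| Both | 1.44 | 27.6% | 1679 |

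**Missed cases, unequal.** For a true ratio of 2, missing 10% in controls and 30% in the Nerivio group gives 2 × 0.7/0.9 = 1.56. The reverse gives 2 × 0.9/0.7 = 2.57. Unequal loss is possible because Study Design and Recruitment brings in one group through the device's user base and the other through clinic referral.

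**The case against.** A reader might infer that both weaknesses bias the endpoint towards no difference and that the plan then counts this as success. The documents do not support that.

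- **Direction depends on scale and on group.** Endpoint 4 is a percentage. Equal unrelated findings leave the difference in percentages intact, and equal missed cases leave the ratio intact. Unequal loss can push the result either way.
- **The success rule belongs elsewhere.** "If the null hypothesis is not rejected, the study will be deemed successful" follows hypotheses written for mean gestational age. Endpoint 4 has only the aim of showing no difference, with no decision rule.
- **Loss of terminated cases is possible, not certain.** With no skip rule shown, a woman with a termination may see Q44 and answer Yes, and Q22 already captures some fetal causes of miscarriage. The documents give no count of terminations or late fetal deaths, and there may be few.
- **Sparse events are the larger weakness.** For a doubling from 3%, even a clean endpoint has only 19% power at 114 per group and 53.5% at 400 (normal approximation).
- **An outcome of any diagnosed defect is defensible.** It avoids judging relatedness from mothers' descriptions.
- **Recontact is conceivable**, since payment is sent to an email address. The plan does not provide for it, and the consent terms are not in the documents reviewed.

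All of this stands and limits the claim. It does not remove the gap: type and timing are not recorded, and terminations and late fetal deaths carry no reason.

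**Conclusion.** The point holds as a measurement weakness that lowers interpretability and power. It does not establish a bias in a known direction. Endpoint 4 cannot be broken down by type or timing, and its coverage of terminated and lost pregnancies is uncertain.

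Under the assumed 3% versus 9% with 4% unrelated findings, power drops by about 17 percentage points at 114 per group (50% to 33%) and about 14 at 400 (96% to 82%). These sizes rest on assumed rates and on equal error in both groups. The tripling is a large effect, and power for a doubling is lower throughout. The loss of power matters because the endpoint is meant to demonstrate no difference and has no margin. The change should be made, though it bears on a secondary endpoint and not on the primary analysis.

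**What to change.** 1. Reword Q44 to: *Was the baby or fetus diagnosed with any birth defect, before or after birth?* Show it for every pregnancy outcome, including termination, miscarriage and late fetal death.
2. After a Yes, ask which defect it was, when it was diagnosed, and whether it led to termination or loss.
3. Keep any diagnosed defect as endpoint 4, and state the denominator as all study pregnancies.
4. Report structural, chromosomal and minor findings separately, each with the between-group difference and its confidence interval.

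**Cost.** The added questions appear only after a Yes. Under the assumed rates at 400 per group, that is up to 0.13 × 400 = 52 answers in a group with 4% unrelated findings, or 0.15 × 400 = 60 with 6%. Some coding time is needed. The change makes the reported cases interpretable, but it does not cure the low power for rare defects, and a finding of no difference would still need cautious reading.
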